[Protocol for Clinical Trial]

The effects of direct swallowing training and oral sensorimotor stimulation in preterm infants

2015.07

NCT02508571

Table of Contents

1. Title of the Clinical Trial	5
2. Name and Address of the Clinical Trial Institution	5
3. Study Period	5
4. Objectives of the Study	5
5. Study Design	5
6. Study Participants	5
7. Study procedures	7
8. Study evaluation	12
9. Dropout	15
10. References	16

[Clinical Trial Overview]

Clinical Trial Title	The effects of direct swallowing training and oral sensorimotor stimulation in preterm infants
Objective of the Clinical Trial	This study aims to evaluate whether the application of direct swallowing training (DST) and oral sensorimotor stimulation (OSMS) in preterm infants preparing for the transition from tube feeding to oral feeding shortens the time required for complete oral feeding and improves oral feeding skills. Additionally, the study will assess the long-term impact of oral feeding

Protocol_DST and OSMS_oral feeding performance

	interventions in the neonatal intensive care unit (NICU) on developmental outcomes and dietary habits.
Phase of the Clinical Trial	Prospective, blind, controlled, randomized trial
Clinical Trial Institution	Seoul National University Hospital
Principal Investigator	[name], Department of Pediatrics, Seoul National University College of Medicine
Study Design	single-center, prospective, open-label, controlled, randomized study
Study participants	
 -Gestational age at birth < 32+0 weeks -Eligible for respiratory support using heated humidified high-flow nasal cannula (HHFN) or equivalent, within 33+0 weeks -Infants who have been progressing with tube feeding at a volume of 120 ml/kg/day or more -Informed consent obtained from parents or legal guardians
Number of participants	189
Study methodology	
In this study, preterm infants who are receiving adequate tube feeding and have been discontinued from continuous positive airway pressure (CPAP) for at least 48 hours will be divided into three groups:
 
 - Control Group -DST Group (Direct Swallowing Training) -DST + OSMS Group (Direct Swallowing Training + Oral Sensorimotor Stimulation) 
Each group will receive its respective intervention.

Study period	From IRB approval date in 2015 to December 30, 2025.
Outcomes	
 1. Time from initiation of oral feeding to full oral feeding 2. Oral feeding performance 3. Neonatal Oral Motor Assessment Scale (NOMAS) 4. Bayley Scales of Infant and Toddler Development, Third Edition: CA 18-24months 5. Korean Version of MacArthur-Bates Communicative Development Inventories (K M-B CDI): postnatal age 36 ± 2 months 6. Korean-Wechsler Preschool and Primary Scale of Intelligence (K-WPPSI)-Fourth Edition: 4:0~4:11 years 7. Korean Developmental Screening Test for Infants (K-DST) : postnatal age 48 ± 3 months 8. Strengths and Difficulties Questionnaire (SDQ) : postnatal age 48 ± 3

Protocol_DST and OSMS_oral feeding performance

	months 9. Behavioral Pediatric Feeding Assessment Scale (BPFAS) : postnatal age 48 ± 3 months
Expected outcomes and potential impact	It is expected that the group receiving DST will show improved oral feeding abilities compared to the control group. Furthermore, the combination of OSMS with DST is anticipated to have a synergistic effect, further enhancing oral feeding skills. Additionally, it is expected that interventions during the neonatal period will have a lasting impact on long-term development and feeding behaviors.

Protocol_DST and OSMS_oral feeding performance

1. Title of the clinical trial

The effects of direct swallowing training and oral sensorimotor stimulation in preterm infants

2. Name and Address of the Clinical Trial Institution

Institution Name: Seoul National University Children's Hospital
Address: [name]

3. Study period

From IRB approval date in 2015 to December 30, 2025.

4. Objectives of study

We will observe whether the application of direct swallowing training (DST) and oral sensorimotor stimulation (OSMS) to preterm infants, preparing for the transition from gavage feeding to oral feeding, shortens the period of transition to full oral feeding and improves oral feeding ability. Additionally, we will evaluate the long-term impacts of oral feeding interventions in the neonatal intensive care unit (NICU) on development, feeding behaviors, and other related factors.

5. Study Design

single-center, prospective, open-label, controlled, randomized study

6. Study participants

6.1 Participants

Preterm infants with a gestational age of less than 32+0 weeks, admitted to the NICU at Seoul National University Children's Hospital, who can be administered respiratory support with heated, humidified high-flow nasal cannula within 33+0 weeks and who have received gavage feeding of at least 120 ml/kg/d.

6.2 Target sample size and rationale for calculation

The primary objective of this study is to determine whether there is a difference in the time taken to reach full oral feeding, from the initiation of oral feeding, when DST and OSMS are applied to preterm infants preparing for the transition from gavage feeding to oral feeding.

To calculate the sample size required to achieve the research objective, the following assumptions are made:

Protocol_DST and OSMS_oral feeding performance

(1) Level of significance (α): 0.0167 (two-tailed test).

When comparing the control group with the DST group, the control group with the DST + OSMS group, and the DST group with the DST + OSMS group, there is an issue of multiple comparisons. To address this, Bonferroni correction is applied. The significance level used is $0.05/3 = 0.0167$.

(2) Group ratio: Control group : DST group : DST + OSMS group = 1 : 1 : 1.

(3) Type II error (β): 0.20, maintaining a test power of 80%.

(4) Primary outcome: Days from start to full oral feeding (SOF-FOF).

(5) The hypothesis of the study is as follows:

[Hypothesis 1]

Null hypothesis: There is no difference in SOF-FOF days between the control group and the DST group.

Alternative hypothesis: There is a difference in SOF-FOF days between the control group and the DST group.

[Hypothesis 2]

Null hypothesis: There is no difference in SOF-FOF days between the control group and the DST + OSMS group.

Alternative hypothesis: There is a difference in SOF-FOF days between the control group and the DST + OSMS group.

[Hypothesis 3]

Null hypothesis: There is no difference in SOF-FOF days between the DST group and the DST + OSMS group.

Alternative hypothesis: There is a difference in SOF-FOF days between the DST group and the DST + OSMS group.

(6) Sample size calculation method: The PASS program (Power Analysis and Sample Size software; <http://www.ncss.com>) will be used.

Based on existing research data (16, 18), the average SOF-FOF days for each group were assumed as follows: Control group 20.8 days, DST group 14.6 days, and DST + OSMS group 10.0 days. The pooled standard deviation was calculated to be 7.19. With a significance level of 1.67% and a two-tailed test, the required sample size for 80% power is 56 participants per group, for a total of 168 participants.

Protocol_DST and OSMS_oral feeding performance

Assuming a 10% dropout rate, the final sample size, accounting for dropouts, is 189 participants.

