8.4.2 Statistical Analysis Methods

- Statistical Software: SPSS for Windows (version 19.0)
- Continuous Variables: Mann-Whitney U test, One-way ANOVA
- Categorical Variables: Chi-square test, Fisher's exact test
- Evaluation of the Effect of Interventions on Primary and Secondary Outcomes:
 - Two-way analysis of variance
 - Repeated measures analysis of variance
 - Post-hoc analysis, if necessary
- Univariate/Multivariate Analysis: Binary and multiple logistic regression analysis
- Unless otherwise specified, all statistical tests will be conducted at a two-sided significance level of 0.05.

9. Drop out

<Criteria for Clinical Trial Dropout>

- When the guardian requests discontinuation of the clinical trial or withdraws consent for participation.
- When the participant experiences respiratory deterioration during the trial period, requiring the use of a respiratory device beyond nasal positive pressure ventilation.
- When the participant experiences gastrointestinal deterioration during the trial period, necessitating fasting for more than 48 hours.
- When a serious adverse event occurs.

10. References

- 1) American Academy of Pediatrics Committee on Fetus and Newborn. Hospital discharge of the high-risk neonate. *Pediatrics* 2008;122:1119-26.
- 2) Bragdon DB. A basis for the nursing management of feeding the premature infant. *JOGN Nurs* 1983;12(3 Suppl):51s-7s.
- 3) Gryboski JD. Suck and swallow in the premature infant. *Pediatrics* 1969;43:96-102.
- 6) Bingham PM. Deprivation and dysphagia in premature infants. *J Child Neurol* 2009;24:743-9.

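### Section 6.2 tests the three primary comparisons with plain Bonferroni; Holm keeps the same 5% familywise error and has more power at the same sample size

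*Combined protocol and SAP*

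**What the plan says.** Section 6.2 defines three two-sided hypotheses on SOF-FOF days: control versus DST, control versus DST + OSMS, and DST versus DST + OSMS. The third reads "Alternative hypothesis: There is a difference in SOF-FOF days between the DST group and the DST + OSMS group". On multiplicity the section states "To address this, Bonferroni correction is applied" and sets 0.05/3 = 0.0167 for each comparison. The planning means are "Control group 20.8 days, DST group 14.6 days, and DST + OSMS group 10.0 days", and "The pooled standard deviation was calculated to be 7.19". It concludes that "the required sample size for 80% power is 56 participants per group", which makes 168, or 189 with 10% dropout.

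Section 8.4.2 repeats neither the correction nor the 0.0167. It lists Mann-Whitney and one-way ANOVA for continuous variables. For intervention effects on the outcomes it lists "Two-way analysis of variance", repeated measures ANOVA and "Post-hoc analysis, if necessary". No single test is assigned to SOF-FOF. The section ends: "Unless otherwise specified, all statistical tests will be conducted at a two-sided significance level of 0.05". That default gives way to a level specified elsewhere, so 6.2 governs the primary comparisons. Section 8.4.2 has a gap in wording here, but it does not contradict 6.2.

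**The concern.** Single-step Bonferroni holds every comparison at 0.0167 even after the others have been rejected. Holm compares the smallest p-value with 0.0167, the next with 0.025 and the largest with 0.05, and stops at the first failure. It needs only valid p-values, as Bonferroni does, and it can never reject less.

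The comparison that stands to gain is DST versus DST + OSMS. It has the smallest assumed difference, so it drives the sample size, and it is the only one that isolates what OSMS adds to DST. Under the plan's own means Bonferroni misses that effect about 17% of the time and Holm about 8%.

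**Working it through.** **Inputs (section 6.2).** Means 20.8, 14.6 and 10.0 days; SD 7.19; two-sided 0.05/3 per comparison; 80% power; 56 per arm. The differences are 20.8 − 14.6 = 6.2, 20.8 − 10.0 = 10.8 and 14.6 − 10.0 = 4.6.

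**Reproducing the sample size.** For the 4.6-day difference:
- Normal approximation: n = 2[SD(z for 0.05/3 two-sided + z for 80% power)/4.6]² = 51.2, so 52 per arm.
- Exact t-test: 53 per arm.
- Inflating 53 by π/3, the Mann-Whitney efficiency adjustment for normal data: 55.5, so 56. This matches the plan, although 6.2 names only the software and not the test.
- Dropout: 56/0.9 = 62.2, rounded up to 63; 3 × 63 = 189, as stated.

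**Power under Bonferroni.** The standard error is 7.19 × √(2/56) = 1.359, and the noncentrality is 4.6/1.359 = 3.39. The exact t-test power at 0.05/3 is 82.8%.

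**What Holm can reach.** If the other two comparisons are rejected first, DST versus DST + OSMS is tested at 0.05, where exact t-test power is 91.9%. At 0.05/3 the other two already have 98.3% and almost 100% power, so Holm should come very close to that ceiling.

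**Simulation.** 100,000 three-arm trials per scenario, 56 per arm, SD 7.19 in every arm. The gamma and lognormal cases are an assumption, with the plan's means and SD. They were added because a normal distribution with mean 10.0 and SD 7.19 puts about 8% of values below zero days. F-gated means pairwise tests at 0.05 after a significant one-way F-test. Power for DST versus DST + OSMS:

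| Means (control/DST/DST + OSMS) | Data | Test | Bonferroni | Holm | F-gated |
|---|---|---|---|---|---|
| 20.8/14.6/10.0 | normal | t | 83.0% | 91.9% | 91.9% |
| | normal | Mann-Whitney | 80.7% | 90.4% | 90.4% |
| | gamma | t | 82.5% | 91.4% | 91.4% |
| | gamma | Mann-Whitney | 92.4% | 97.0% | 97.0% |
| | lognormal | t | 82.1% | 90.6% | 90.6% |
| | lognormal | Mann-Whitney | 97.1% | 99.1% | 99.1% |
| 14.6/14.6/10.0 | normal | t | 82.9% | 85.6% | 90.2% |
| | normal | Mann-Whitney | 80.6% | 83.5% | 89.0% |
| | gamma | t | 82.1% | 84.6% | 89.6% |
| | gamma | Mann-Whitney | 92.2% | 93.8% | 92.3% |
| | lognormal | t | 82.2% | 84.3% | 89.2% |
| | lognormal | Mann-Whitney | 97.2% | 97.9% | 92.4% |

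The chance of rejecting all three under the plan's means (normal data) rises from 81.3% to 91.4% with t-tests and from 78.5% to 89.7% with Mann-Whitney. No Bonferroni rejection was lost under Holm.

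**Error control (normal data, t-tests).** With no differences at all, any rejection occurs in 4.3% of trials under both Bonferroni and Holm, and in 4.9% under the F-gate. With means 20.8/14.6/14.6, so that OSMS adds nothing, DST versus DST + OSMS is falsely rejected in 1.7% of trials under Bonferroni and 4.7% to 4.8% under Holm.

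**Intervals (normal data, t-tests).** Under the plan's means, Holm rejects while the Bonferroni 98.3% interval still includes zero in 8.9% of trials; 0.089/0.919 = 9.7% of Holm's rejections. An unadjusted 95% interval always excludes zero when Holm rejects. It also excludes zero without a Holm rejection in 0.0% of trials under the plan's means, 6.3% at 14.6/14.6/10.0, and 3.2% with no differences.

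**The case against.** The strongest reply is that nothing is broken: Bonferroni is valid and delivers 83% (t) or 81% (Mann-Whitney) against a target of 80%. That is right, and the point is one of efficiency only. Other objections have some force:

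- **Actual error rises.** If OSMS adds nothing, false rejection of DST versus DST + OSMS goes from 1.7% to about 4.8%. It stays within the 5% the plan allows, but it is not zero cost.
- **Holm is not the most powerful option.** With three pairwise hypotheses, one true difference leaves at most one of the other two nulls true, so Shaffer's step-down levels (0.0167, 0.05, 0.05) also hold 5%. They give 88.9% against Holm's 85.6% at 14.6/14.6/10.0 and tie with Holm under the plan's means. This does not rescue plain Bonferroni, which Holm already dominates.
- **The baseline could be read differently.** The ANOVA and post-hoc entries in 8.4.2 could be read as an F-test followed by comparisons. Holm gains nothing over F-gated t-tests. But 6.2 states Bonferroni explicitly, and no other multiplicity rule appears in the documents.
- **The larger gain depends on the means.** The 9 points arise because the other two comparisons are almost always rejected. The 3-point figure assumes control and DST both at 14.6 days. At 20.8/20.8/10.0 the comparison has about 100% power either way and the gain is nil.
- **Timing.** The study period starts in 2015 and the reference list includes a 2019 paper. The documents do not show whether outcomes by group have been seen.

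**Conclusion.** The point holds as a recommended improvement to a valid plan. Against the method that 6.2 states, Holm keeps familywise error at 5%, loses no rejection and needs no more infants. For DST versus DST + OSMS with t-tests on normal data, the gain is about 9 points under the plan's means (83% to 92%) and about 3 points at 14.6/14.6/10.0.

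Across the tests and distributions tried, the gain is 2 to 10 points under the plan's means and about 1 to 3 points at 14.6/14.6/10.0. It is smallest with Mann-Whitney on skewed data, where Bonferroni power is already high. These figures assume 56 evaluable infants per arm and a common SD of 7.19.

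**What to change.** In both 6.2 and 8.4.2, state that the primary analysis is the three pairwise SOF-FOF comparisons, all carried out with one named two-sample test, with p-values adjusted by Holm at a familywise two-sided 0.05. The sponsor should fill in the test the trial was sized on. Holm applies unchanged to the three p-values of any valid test, including contrasts from the two-way ANOVA.

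In 8.4.2, remove the condition on post-hoc comparisons for the primary outcome and limit the 0.05 default to all other tests. Keep 189, with Bonferroni as the conservative planning basis. State that Holm-adjusted p-values decide significance, and report unadjusted 95% intervals labelled as descriptive.

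The cost is wording only, with no change to sample size, visits or data. The drawback is the lack of a simple matching interval, which is why the descriptive label is needed. The edit must be dated and fixed before anyone sees outcome data by group. If that point has passed, Bonferroni as stated in 6.2 should stay as the primary rule.

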6.3 Recruit method for study participants

The guardians of eligible participants will be approached to obtain their consent for participation in the study. Detailed information about the study will be provided to them, including its objectives, procedures, potential risks, and benefits. Informed consent will be obtained from the guardians before the preterm infants are enrolled in the study. All necessary ethical considerations and guidelines will be followed during the recruitment process, ensuring the confidentiality and protection of the participants' privacy.

6.4 Inclusion and Exclusion criteria for enrolment

6.4.1. Inclusion criteria

- (1) Preterm infants with a gestational age of less than 32+0 weeks.
- (2) Infants currently receiving sufficient tube feeding (at least 120 ml/kg/day).
- (3) Infants who can be treated with heated, humidified high-flow nasal cannula (HFNC) within 33+0 weeks.
- (4) Infants who only have feeding-related issues remaining, with no need for special medical treatment.
- (5) Infants whose parents voluntarily sign the informed consent form for participation in the study.

6.4.2. Exclusion criteria

- (1) Infants with major congenital malformations, such as those affecting the face, central nervous system, gastrointestinal system, or heart.
- (2) Infants with gastrointestinal complications.
- (3) Infants with chronic medical conditions, such as Grade 3 or higher intraventricular hemorrhage (according to the classification by Papile et al), periventricular leukomalacia, or those who have undergone surgical treatment for necrotizing enterocolitis.

7. Study procedures

7.1 Screening

Evaluation items: gestational age at birth, participant consent, assessment of inclusion/exclusion criteria

7.2 Randomization

In this study, eligible participants who meet all the inclusion criteria will be randomly assigned in a

Protocol_DST and OSMS_oral feeding performance

1:1:1 ratio to the control group, the DST group, or the DST + OSMS group. However, randomization will be stratified by gestational age and sex.

The randomization will be done using a block randomization method with block sizes of 3 and 6, generated through SAS 9.2. The randomization process will be managed via the MRCC website (<http://mrcc.snu.ac.kr>) using web-based randomization.

The detailed randomization procedure is as follows:

- Study coordinators will be provided with an ID and password for randomization.
- The study coordinators will log in to the MRCC website (<http://mrcc.snu.ac.kr>) and access the randomization screen.
- The study coordinator will enter the participant's basic information, test results, inclusion/exclusion criteria, and other relevant data, and click the confirmation button.
- If the participant is eligible, a randomization number will appear on the screen.
- The randomization screen will be printed, and one copy will be kept for records.
- The study coordinator will use the assigned randomization number to prescribe the corresponding intervention.

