8.4 Statistical analysis methods

8.4.1. Definition of Analysis Sets

- ITT Analysis Set (Intent-to-Treat): Includes data from all pediatric patients who received at least one session of oral rehabilitation therapy and had at least one assessment of the outcome variable.
- FAS Analysis Set (Full Analysis Set): Includes data from the ITT set, excluding patients who did not meet the eligibility criteria or failed to undergo the primary outcome assessment.
- PP Analysis Set (Per-Protocol): Includes data from the ITT set, specifically from patients who strictly adhered to the clinical trial protocol by completing direct swallowing training or both direct swallowing training and sensory-motor stimulation therapy, with outcome variables assessed.

This study will conduct ITT, FAS, and PP analyses, with FAS analysis being the primary approach.

* Subgroup Analysis: Subgroup analysis will be performed based on gestational age, birth weight, and bronchopulmonary dysplasia.

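### Randomisation is stratified by gestational age and sex, but no test of the primary outcome is stated to account for either; saying so in 8.4.2 costs almost nothing and narrows the intervals if the factors are prognostic

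*Combined protocol and SAP*

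**What the plan says.** Section 7.2 assigns infants 1:1:1 in blocks of 3 and 6 and says that "randomization will be stratified by gestational age and sex". It gives no gestational-age bands.

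Section 8.4.2 lists methods without tying any of them to a named covariate:

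- "Continuous Variables: Mann-Whitney U test, One-way ANOVA".
- Under "Evaluation of the Effect of Interventions on Primary and Secondary Outcomes": "Two-way analysis of variance", repeated measures ANOVA and, if needed, post-hoc analysis.
- For univariate and multivariate work: "Binary and multiple logistic regression analysis".

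Gestational age appears once more in the analysis text, in 8.4.1: "Subgroup analysis will be performed based on gestational age, birth weight, and bronchopulmonary dysplasia". Sex appears nowhere in 8.4.

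Section 6.2 sets the primary comparisons: three pairwise tests of SOF-FOF days at two-sided 0.0167, assumed means of 20.8, 14.6 and 10.0 days, and 56 infants per group. It adds: "The pooled standard deviation was calculated to be 7.19".

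**The concern.** Stratified allocation balances the arms on the stratifying factors. If those factors predict the outcome, the true variance of a between-arm difference is smaller than an analysis that ignores them will estimate. The usual remedy is to carry the factors into the analysis.

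Nothing in 8.4.2 says that this will happen. Mann-Whitney and one-way ANOVA have no place for a covariate. Logistic regression does not fit an outcome in days. A subgroup analysis by gestational age is not an adjustment. The two-way ANOVA has room for a second factor, but that factor could be gestational age, sex, the combined stratum or something else.

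At stake are the width of the intervals and the power of the hardest comparison, DST versus DST+OSMS, which tests whether OSMS adds anything to DST. A smaller matter is that, with the second factor unnamed, whether and how to adjust could be settled after results are known.

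**Working it through.** **Inputs from section 6.2.** SD 7.19; 56 per arm; alpha 0.05/3 = 0.0167 two-sided, so z = 2.394. Pairwise differences: 20.8 − 14.6 = 6.2, 20.8 − 10.0 = 10.8 and 14.6 − 10.0 = 4.6 days.

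**The plan's own figure.** For 4.6 days at 80% power, the normal approximation gives n = 2 × (2.394 + 0.842)² × 7.19² / 4.6² = 51.2, so 52 per group. The t-test gives 53. Inflating for Mann-Whitney (efficiency 3/π) gives 53 × π/3 = 55.5, so 56, the stated number. With 10% dropout, 56/0.9 = 62.2, so 63, and 3 × 63 = 189, as stated. The size therefore comes from an unadjusted two-group calculation. That it was meant for a rank test is an inference; the protocol names only the software.

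**Assumptions.** R² is the share of outcome variance explained by gestational age and sex. The documents give no value, so 0 to 0.2 is assumed. The share of that explained variance captured by the randomisation strata, s, is taken as 0.75 to 1. The SD of 7.19 is treated as the total SD, strata as balanced, and the model as linear in days.

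**Formulas.** SE = 7.19 × √(2/56) = 1.359.

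- Half-width, unadjusted: 2.394 × 1.359 = 3.25 days. Adjusted: 3.25 × √(1 − R²).
- Power, adjusted: Φ(4.6 / (1.359 × √(1 − R²)) − 2.394).
- Power, unadjusted after stratified allocation: Φ((4.6/1.359 − 2.394) / √(1 − s·R²)).
- Type I error, unadjusted: 2 × P(Z > 2.394 / √(1 − s·R²)).

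Example at R² = 0.2. Adjusted: 1.359 × √0.8 = 1.215 and 4.6/1.215 − 2.394 = 1.39, so 91.8%. Unadjusted with s = 1: 0.991/0.894 = 1.11, so 86.6%.

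| R² | Adjusted half-width (days) | Unadjusted power, 4.6 days | Adjusted power | Unadjusted type I error |
|---|---|---|---|---|
| 0 | 3.25 | 83.9% | 83.9% | 0.0167 |
| 0.05 | 3.17 | 84.4–84.6% | 86.0% | 0.0147–0.0140 |
| 0.1 | 3.09 | 84.9–85.2% | 88.0% | 0.0128–0.0116 |
| 0.2 | 2.91 | 85.9–86.6% | 91.8% | 0.0094–0.0074 |

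(Ranges run from s = 0.75 to s = 1.)

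**Other comparisons.** On the same approximation, power is already 98.5% or more for 6.2 days and about 100% for 10.8 days.

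**If the two-way ANOVA already uses the combined stratum** (s = 0.75), the half-width is 3.13 days at R² 0.1 and 3.00 at 0.2, with power 87.0% and 89.9%. Replacing the stratum by continuous gestational age plus sex then adds 88.0 − 87.0 = 1.0 and 91.8 − 89.9 = 1.9 points.

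**Cost if neither factor is prognostic.** On the t distribution, two extra model terms (110 to 108 degrees of freedom) take power from 82.82% to 82.80%, about 0.02 points.

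**Simulation check.** 10,000 runs, 168 infants, with these assumptions: gestational age uniform over 24 to 32 weeks with a linear effect, sex not prognostic, strata cut at 28 weeks by sex. Power unadjusted / stratum-adjusted / continuous gestational age plus sex was 84.6/86.7/87.8% at R² 0.1 and 84.8/89.2/91.3% at 0.2 (Monte Carlo SE about 0.4 points), in line with the formulas.

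**The case against.** **The gap may not exist.** The two-way ANOVA is listed for the primary outcome, and in a trial randomised within gestational-age-by-sex strata, the combined stratum is a natural second factor. It would hold both stratifiers at once. This stands: a reader might infer that the primary test ignores the strata, and the documents do not show that. They do not show the opposite either. On the favourable reading the factor still has to be named and the bands stated, but only 1 to 2 points of power remain to be gained.

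**The gain rests on an assumed R².** This also stands. Gestational age is treated as relevant, being both a stratifier and a subgroup factor; for sex, stratification is the only sign. At R² 0.05 the half-width falls by just 0.08 days. The simulation illustrates the size and is not evidence for it.

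**The baseline may be the wrong test.** If the pairwise test is Mann-Whitney, as the sample size suggests, power for 4.6 days is about 81%; for a t-test it is about 83%. The adjusted figures above do not apply to a rank test. For the same reason, a reader might infer that adjustment requires a linear model on untransformed days. It does not: the outcome is a duration, a rank test is listed, and moving from ranks to means would change the hypothesis tested.

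**It is only a refinement.** It is true that no error of validity is involved, and that the point sits within the wider gap that no single primary test is designated. It still merits a line of text, because the loss when the factors are prognostic is avoidable and the cost when they are not is negligible.

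**Conclusion.** The point holds as an improvement in efficiency and pre-specification. Section 8.4.2 does not state that any test of SOF-FOF days accounts for the factors used to stratify allocation. Should the test ignore them and should they be prognostic, it is conservative and its intervals are wider than the data allow.

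A reader might go further and infer inflated false positives or an underpowered trial. Neither follows: ignoring the strata lowers the type I error below 0.0167, and power for the smallest assumed difference stays above 80% throughout the range examined.

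The benefit falls on DST versus DST+OSMS: nothing at R² 0, about 3 points of power at 0.1 and 5 to 6 points at 0.2, if the comparison would otherwise be unadjusted. Confidence is moderate, because the prognostic strength, the share captured by the strata and the linear model in days are all assumed, and because the intended second factor of the ANOVA is unknown.

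**What to change.** State in 8.4.2 that the primary comparison of SOF-FOF days accounts for gestational age and sex, in the form that suits whichever test is designated:

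- linear model or ANCOVA: arm, gestational age at birth (continuous) and sex;
- two-way ANOVA: arm and the combined gestational-age-by-sex stratum, named as the second factor;
- rank test (van Elteren) or time-to-event test: stratified by sex and by the gestational-age bands of the randomisation system.

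Test each of the three pairwise comparisons at 0.0167, as 6.2 already plans. With a mean-based model, report adjusted differences with 98.33% intervals. Give the unadjusted analysis as sensitivity. Choosing between a mean-based, rank or time-to-event test is outside this fix.

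**Cost.** No extra infants, visits or data. Section 7.1 lists "Evaluation items: gestational age at birth", and 8.1 records both gestational age and sex. The linear model needs SAP wording only; the stratified options also need the bands copied from the randomisation system, since 7.2 omits them. The change should be fixed before outcome data by arm are seen. The study period begins in 2015 and the reference list includes a 2019 paper, so the text was edited after the planned start; the documents do not show whether outcome data had been examined by then, and the sponsor should state this with the change.
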